## LIST OF ABBREVIATIONS

AE	adverse event
ALT	alanine aminotransferase
AST	aspartate aminotransferase
BUN	blood urea nitrogen
BZA	Bazedoxifene acetate
CFR	Code of Federal Regulations
CVLT-II	California Verbal Learning Test-II
eCRF	Electronic Case Report Form
DMC	Data Monitoring Committee
DSMB	Data Safety Monitoring Board
EAE	Experimental Autoimmune Encephalomyelitis
EDSS	Expanded Disability Status Scale
EEG	Electroencephalogram
FDA	Food and Drug Administration
GCP	Good Clinical Practice
GGT	gamma-glutamyl transferase
HIPAA	Health Insurance Portability and Accountability Act of 1996
HPLC-MS/MS	High-performance Liquid Chromatographic-tandem mass spectrometric method
ICF	informed consent form
ICH	International Conference on Harmonisation
IEC	Independent Ethics Committee
IRB	Institutional Review Board
IV	intravenous
LDH	lactate dehydrogenase
mEq	milliequivalent
MFIS	Modified Fatigue Impact Scale
MfVEP	Multi Focal Visual Evoked Potential
MRI	Magnetic Resonance Imaging
MS	Multiple Sclerosis
MSWS-12	Multiple Sclerosis Walking Scale
OCT	Optical Coherence Tomography
OPC	Oligodendrocyte progenitor cells
PI	Principal Investigator
RNFL	Retinal Nerve Fiber Layer

RRMS	Relapsing Remitting Multiple Sclerosis
SAE	serious adverse experience
SDMT	Symbol Digit Modality Test
SERM	Selective Estrogen Receptor Modulator
T25W	Timed 25-foot Walk
TUG	Timed-Up-and-Go
VEP	Visual Evoked Potential

## PROTOCOL SYNOPSIS

TITLE	Bazedoxifene acetate as a remyelinating therapy for patients with MS
SPONSOR	[name] [name]
FUNDING ORGANIZATION	Sherak foundation
NUMBER OF SITES	1
RATIONALE	
Multiple Sclerosis (MS) is a chronic neurologic disorder characterized by the loss of myelin, which results in disruption of nerve signal, damage to axons, and, ultimately, neurodegeneration. In order to treat MS, new methods for promoting repair (remyelination) are sorely needed.
 
There is a strong preclinical (including EAE) and epidemiologic rationale for investigating the remyelinating potential of estrogenic compounds, including evidence of endogenous (puberty, postpartum periods) and exogenous hormonal influences on MS risk and course. MS affects 3 times more women than men, and disease course in women appears overall less aggressive (on MRI, fewer T2-hyperintense demyelinated lesions develop into axonal destruction visualized as hypointense T1 "black holes").
 
BZA, a third-generation SERM with extensive safety data in humans, was identified in a novel high-throughput screen (BIMA screen) for compounds capable of promoting remyelination. Subsequent analysis validated BZA's remyelinating effect in vitro and in vivo following demyelinating insult. Given strong pre-clinical support for BZA's remyelinating potential, and the clinical success of other compounds identified using the BIMA screen (Green et al., 2017), we propose the investigation of BZA as a remyelinating therapy in MS.

STUDY DESIGN	This is a single-center, double blind, randomized, controlled, delayed-start Phase 2 clinical trial investigating the remyelinating effects of BZA relative to placebo.
PRIMARY OBJECTIVE	The primary objective is to evaluate the efficacy of BZA relative to placebo for reducing P100 latencies on full field transient pattern reversal visual evoked potentials at 90 days in a double-blinded trial (1st 90 days in Group A versus 1st 90 days of Group B.)

SECONDARY OBJECTIVES	
 
• The first key secondary objective is to assess whether latency delay at 180 days decreases to a greater extent in Group A (exposed to BZA for 90 days during both Stage 1 and Stage 2) when compared to Group B (exposed to placebo during Stage 1 and BZA for only 90 days during Stage 2).
 
• The second key secondary objective is to demonstrate the tolerability of BZA in this population. This will include special focus with regards to fatigue as this is a major symptom for patients suffering from multiple sclerosis.
 
• The third key secondary objective is to document the safety of BZA in this population of patients.
 
• The fourth key secondary objective of this study is to help assess which secondary and tertiary outcomes are likely to be informative for future remyelinating trials in multiple sclerosis.
 

NUMBER OF SUBJECTS	50
SUBJECT SELECTION CRITERIA	
Inclusion Criteria:
 
 
1. Relapsing remitting Multiple Sclerosis by 2017 Revised McDonald Criteria
 
2. Women aged 45-65 or 40+ post-menopausal.
 
3. Latency delay > 118 milliseconds on baseline full-field transient pattern reversal VEP in at least one eye (electrophysiological evidence of demyelination)
 
4. RNFL > 70 microns on SD-OCT in the same eye meeting criteria for latency delay (sufficient axons)
 
5. Stable immunomodulatory therapy – no switch or planned switch in > 6 months and no change in doses in 30 days prior to screening
 
6. Use of contraceptive method with <math>\leq 1\%</math> failure rate during period of trial if premenopausal
 
7. Understand and sign informed consent.
 
8. EDSS 0-6.0 (inclusive)
 
 
Exclusion Criteria:
 
 
1. Multiple Sclerosis disease duration > 25 years
 
2. Optic neuritis in prior 6 months
 
3. Known optic neuritis in involved eye <math>\geq 10</math> years ago
 
4. Major ophthalmologic disease/Concomitant ophthalmologic disorders (e.g. diabetes, macular degeneration, glaucoma, severe myopia, etc.).
 
5. Myopia > -7 Diopters (severe myopia)
 
6. Disc hemorrhages in qualifying eye
 
7. No light perception in qualifying eye
 
8. Simultaneous bilateral optic neuritis
 

	
 
9. Cotton wool spots in qualifying eye
 
10. Macular star in qualifying eye
 
11. History of significant cardiac conduction block
 
12. History of cancer (except non-melanoma skin cancer)
 
13. Suicidal ideation or behavior in 6 months prior to baseline
 
14. Pregnancy, breastfeeding, or planning to become pregnant
 
15. Included with other study protocol simultaneously without prior approval
 
16. Concomitant or prior use of any other putative remyelinating therapy as determined by investigator, including but not limited to Clemastine, Duavée, and Tamoxifen.
 
17. Serum creatinine > 1.5mg/dL; AST, ALT, or alkaline phosphatase > 2 times the upper limit of normal
 
18. History of drug or alcohol abuse within the past year
 
19. Untreated B12 deficiency (as determined by B12 serological assessments and metabolites including methylmalonic acid [MMA] and homocysteine) or untreated hypothyroidism
 
20. Clinically significant cardiac, metabolic, hematologic, hepatic, immunologic, urologic, endocrinologic, neurologic, pulmonary, psychiatric, dermatologic, allergic, renal or other major diseases that in the PI's judgement may affect interpretation of study results or patient safety.
 
21. History of or presence of clinically significant medical illness or laboratory abnormality that, in the opinion of the investigator would preclude participation in the study.
 
22. Patients whose lack of mobility exposes them to an increased risk of venous thromboembolism
 
23. Patients with undiagnosed uterine bleeding
 
24. Patients with unknown, suspected or past history of breast cancer
 
25. Patients with known or suspected estrogen-dependent neoplasia
 
26. Patients with active or a past history of venous thromboembolism
 
27. Patients with active or a past history of arterial thromboembolism
 
28. Patients with known protein C, protein S, or antithrombin deficiency or other known thrombophilic disorders
 
29. Patients with hypersensitivity (angioedema, anaphylaxis) to estrogens, bazedoxifene, or any ingredients
 
30. Patients with known hepatic impairment or disease
 

TEST PRODUCT, DOSE, AND ROUTE	40mg of bazedoxifene acetate (Conbriza) Product will be taken daily via oral administration of 2 20mg Conbriza

OF ADMINISTRATION	tablets for the duration of treatment period (180 days for 'Early-start' group and 90 days for 'Delayed-start' group). Tablets will be over-encapsulated in gelatin capsules for proper blinding.
CONTROL PRODUCT, DOSE AND ROUTE OF ADMINISTRATION	Microcrystalline cellulose placebo Product will be taken daily via oral administration of 2 tablets for duration of the treatment period (first 90 days of 'Delayed-start' group ONLY). Tablets will be over-encapsulated in gelatin capsules for proper blinding.
DURATION OF SUBJECT PARTICIPATION AND DURATION OF STUDY	Subjects will be on study for up to 200 days Screening: 2 weeks Treatment: 6 months The total duration of the study is expected to be 24 months, which includes 18 months for subject recruitment.
CONCOMITANT MEDICATIONS	Allowed: MS disease modifying and symptomatic therapies, antidepressants (no adjustments within 2 months of baseline visit) Prohibited: hormone therapies (estrogen, testosterone, progesterone), hot flash therapies; lamotrigine, oxcarbazepine
EFFICACY EVALUATIONS	This study includes the following efficacy assessments: 
 
Detailed neurological examination, including the determination of EDSS score, will take place at the baseline and 6-month visits.
 
Magnetic Resonance Imaging (MRI) scans will be performed at the baseline, 3-month, & 6-month visits.
 
High and Low Contrast Visual Acuity (2.5% ETDRS) will be assessed at every visit.
 
Optical Coherence Tomography (OCT) will be performed at screening, baseline, and 6-month visits.
 
Full-field Visual Evoked Potential will be performed at every visit.
 
Cone contrast testing will be performed at baseline and 6 month visits.
 
 Note: Prior to each visit, participants should be reminded to bring with them any corrective lenses that they use on a regular basis for reading, distance, or both. If the participant does not have or if they forget their corrective lenses, a pair of trial lenses will be provided during the visit.
PRIMARY ENDPOINT	Remyelination assessed by the reduction of P100 VEP latency
SECONDARY ENDPOINTS	[Imaging]: Whole brain MTR, white matter MTR, white matter fractional anisotropy (FA), and MWF. [Functional]: Low-contrast letter acuity (LCLA)
OTHER EVALUATIONS	

SAFETY EVALUATIONS	
Phone call at week 6 to see if patient is experiencing any unacceptable side effects.
 
When approximately 50% of patients have completed the study through Study Visit 2 (total visit 3), an interim analysis for safety will be conducted by the PI. Serious adverse events will be monitored by the committee on an ongoing basis throughout the study.
 
Incidence of adverse events.

PLANNED INTERIM ANALYSES	When approximately 50% of patients have completed the study through Study Visit 2 (total visit 3), an interim analysis for safety will be conducted by the PI. Serious adverse events will be monitored by the committee on an ongoing basis throughout the study.
STATISTICS Primary Analysis Plan	Data will be analyzed per protocol utilizing an intention to treat approach including all patients randomized to the study for the principal analysis. Loss to follow up will be accounted for using standard statistical methods. The principal analysis will be performed using mixed effects linear regression model controlling for clustering by eye.
Rationale for Number of Subjects	
With 25 patients per group the study has 90% power to detect a 50% relative reduction in latency with BZA compared to placebo at the 3-month outcome for group 1 assuming a two-sided test with alpha = 0.05.
 
Study size may be expanded to compensate for dropouts over the short study period. To maximize study efficiency and resource utilization these subjects will not be enrolled unless necessary.

## 1 BACKGROUND

Here, we propose a Phase II DBRCT, delayed start protocol, to evaluate the effect of bazedoxifene 40mg vs. placebo on promoting remyelination in women with multiple sclerosis (MS), as measured by Visual Evoked Potentials.

Multiple sclerosis (MS) is the most prevalent chronic, non-traumatic neurological disorder among young adults; MS affects approximately 400,000 people in the United States and 2.1 million people around the world. There is no single diagnostic test for MS; diagnoses are made on the recognition of clinical disease patterns and the exclusion of alternatives. Most notably, patients are required to exhibit the spatiotemporal dissemination of lesions, meaning that evidence of prior demyelinating injury must be present at the time of diagnosis. The myelin sheath is an integral accessory to functioning nerve fibers and provides multiple layers of concentric membrane to axons, which serves to increase conduction velocity and reduce energetic cost of action potentials. Myelin loss in MS results in disruption of the nerve signal, axonal damage, and ultimately neurodegeneration. To effectively prevent the downstream effects of myelin injury, novel approaches to promote repair will be required.

There is a strong preclinical (including EAE) and epidemiologic rationale for investigating the remyelinating potential of estrogenic compounds, including evidence of endogenous (puberty, postpartum periods) and exogenous hormonal influences on MS risk and course. MS affects 3 times more women than men, and disease course in women appears overall less aggressive (on MRI, fewer T2-hyperintense demyelinated lesions develop into axonal destruction visualized as hypointense T1 “black holes”). PI [name] has shown that the 10% of MS women with post-menopausal onset of symptoms do not appear to be “protected” from progression typical of their male counterparts. Further, she has shown that MS disease severity may worsen with ovarian aging. This age-related decline in gonadal steroids might represent a *sex-specific* influence on age-related disability progression, and on decreased CNS resilience—including through remyelination—in the face of neuroinflammatory injury.

Selective Estrogen Receptor Modulators (SERMs) provide more tissue-selective, full or partial agonism or antagonism of estrogen receptors (ER $\alpha$  and ER $\beta$ ). It is widely believed that modulation of ER $\alpha$  and/or ER $\beta$  induces neuroprotection through remyelination. Supportive observations include the classic SERM tamoxifen leading to decreased severity of EAE symptoms and of demyelination, and that the potent, selective ER $\beta$  agonist indazole-chloride (Ind-Cl) induces corpus callosum remyelination in the cuprizone-induced demyelination mouse model of MS. However, the SERM compounds currently examined, such as tamoxifen, have significant tolerability limitations (e.g. hot flashes), which limit their clinical application. In contrast, multiple other agents within this class have demonstrated pharmaceutical indications (osteoporosis, cancer prevention) and are more tolerable. Bazedoxifene (BZA) is a SERM recently FDA-approved in combination with conjugated estrogens (CEs) as Duavee. BZA offsets estrogenic stimulation of endometrial and breast tissue, and CE 0.45mg/BZA 20mg is approved for menopausal hot flash relief and osteoporosis prevention, with a favorable tolerability and safety profile. In the brain, limited data suggest that BZA may

counteract inflammation under neurodegenerative conditions by targeting the production and release of pro-inflammatory molecules by glial cells. In a male rat model of transient focal cerebral ischemia, BZA exerted neuroprotective actions mainly in the cortical region, and estradiol at the subcortical level. Further, our pre-published work presented at this year's joint Americas—European Committee for Treatment and Research in Multiple Sclerosis (ACTRIMS—ECTRIMS) conference in Paris, demonstrates that BZA enhances OPC differentiation *in vitro* and *in vivo* and promotes functional remyelination ([name] et al., ECTRIMS 2017).

To date, the clinical remyelinating effects of BZA are unknown.

## 1.1 Overview of Non-Clinical Studies

Screening for small molecules or biologicals that promote remyelination represents a promising avenue for the identification and development of reparative treatments for MS, but a significant hurdle for the rational advancement of compounds identified in screens remains the functional confirmation of myelin repair. Recent technical advances with screening platforms provide us with this unique opportunity to provide insight into the cell autonomous mechanisms for remyelination and address this unmet need in MS.

SERMs have been identified as compounds capable of promoting oligodendrocyte differentiation using several recent unbiased screens for remyelination, including BIMA (Binary Indicant for myelination using Micropillar Arrays), a functional high-throughput screen developed by the Chan Laboratory at UCSF. BIMA involves freestanding micropillar arrays of compressed silica around which myelin rings of membrane wrapping by oligodendroglia can be visualized in cross-section. These micropillars are placed in 96- and 384-well formats, testing therapeutic compounds' direct influences on oligodendroglia without indirect effects from neurons.

Using this high throughput screen, BZA, was identified as a bioactive compound with strong remyelinating potential (platform presentation, AAN 2017 Annual Meeting). Our pre-published work validated this finding *in vitro* and *in vivo*; OPCs were derived from WT P7 rat pups using previously validated methodology (Mei et al., 2014), cultured in isolation, and treated with increasing concentrations (5-500nM) of BZA for 48 hours. At all concentrations (5nM to 500nM) BZA significantly enhanced OPC differentiation and subsequent myelination (platform presentation, AAN 2017 Annual Meeting [44]). Following a lysolecithin induced toxic, focal demyelinating injury to the corpus callosum of 8-week old adult mice, daily BZA delivered via oral gavage resulted in enhanced differentiation and an increased number of oligodendrocytes in the lesion area when compared to controls. Given subsequent *in vitro* analysis of BZA's differentiation effect on OPCs isolated from ER $\alpha$  and ER $\beta$  null mice (not shown), which revealed a remyelinating mechanism that is independent of either ER, we performed the same *in vivo* analysis on ER $\alpha$ -ER $\beta$  double knockout mice. Comparable OPC differentiation and remyelination following focal demyelination confirmed that the potent reparative effects of BZA is maintained in the absence of ERs.

## 1.2 Overview of Clinical Studies

**Remyelination.** Recently published work from the collaborating Chan and Green Labs at UCSF, provides strong support for the BIMA screening method's ability to identify remyelinating compounds with strong translational potential. Clemastine, a first-generation antihistamine, which is known to readily cross the blood-brain-barrier and has been available as an 'over the counter' in the U.S. since 1992, was identified using this screen and subsequently tested in a clinical trial

assessing its remyelinating potential in patients with MS. This trial (NCT02040298) used VEP latency, a well-validated measure of remyelination, to gauge Clemastine's therapeutic efficacy over the course of the trial period. To date, this remains the only randomized controlled trial to document efficacy of a remyelinating drug for chronic demyelinating injury in MS (Green et al., 2017). These findings support the investigation of compounds with high translational potential that have been identified in BIMA screens.

*Bazedoxifene in clinical trials.* The recent FDA approval of Duavee (BZA + conjugated estrogens) in the U.S was largely dependent on safety and efficacy data obtained from the Selective estrogens, Menopause, And Response to Therapy (SMART) trials. The first SMART trial, SMART-1, included 3,397 subjects who took at least one dose of the study drug; of this group, 840 participants received the same daily dose of BZA (40 mg) as is outlined in this protocol. At the end of the 2-year study, the incidence of adverse events did not differ significantly when compared to placebo, nor were significant differences observed between the 20 mg and 40 mg BZA groups (Pickar et al., 2009). Subsequent SMART trials underscore the safety of BZA in humans but do not include 40 mg treatment groups, as 20 mg was determined to be the lowest effective dose.

The approval of Conbriza (BZA) in the E.U. and Vivant (BZA) in Asia are also supported by several large-scale Phase I-III clinical trials documenting safety and efficacy. In a 3-year, randomized, placebo-, and active-controlled clinical trial assessing the efficacy of BZA in reducing vertebral fracture risk in postmenopausal women with osteoporosis, more than 3,750 women took daily BZA, 1,872 of them at a daily dose of 40 mg. BZA was well tolerated across all treatment doses over the 3-year period of therapy and was shown to be effective in reducing risk of vertebral fracture, increasing BMD of the hip and spine, and reducing bone turnover (Silverman et al., 2008). Multiple other studies, albeit slightly smaller in scale, include treatment groups where patients received daily 40 mg BZA (Itabashi et al., 2011; Miller et al., 2008; Ronkin et al., 2005) and exhibit a favorable safety and tolerability profile.

## 2 STUDY RATIONALE

BZA is an approved medication in the EU and Japan (Conbriza and Vivant, respectively) for the treatment of postmenopausal osteoporosis in women at increased risk of fracture. Multiple longitudinal, multicenter Phase I-III trials have unequivocally supported the use of BZA in human populations matching our inclusion criteria for age and sex (Itabashi et al., 2011; Miller et al., 2008; Pickar et al., 2009; Ronkin et al., 2005; Silverman et al., 2008). We are confident in these safety data, which underscore the minimal assumption of risk, and believe the benefit to individual patients with MS—and the scientific community as a whole—to be far greater than the burden of reasonably occurring treatment emergent adverse reactions.

### 2.1 Risk / Benefit Assessment

The potential benefit resulting from participation in this study is immense—both for the individual and the scientific community. If our preclinical findings, indicating BZA's therapeutic potential for remyelination, are upheld in patients with MS, it will represent a significant step towards fulfilling the long unmet need for reparative treatments. These potential benefits outweigh the minimal risk assumed in participation in this study.

### 3 STUDY OBJECTIVES

#### 3.1 Primary Objective

The primary objective is to evaluate the efficacy of BZA relative to placebo for reducing P100 latencies on full field transient pattern reversal visual evoked potentials at 90 days in a double-blinded trial (1st 90 days in Group A versus 1st 90 days of Group B.)

#### 3.2 Secondary Objectives

- The first key secondary objective is to assess whether latency delay at 180 days decreases to a greater extent in Group A (exposed to BZA for 90 days during both Stage 1 and Stage 2) when compared to Group B (exposed to placebo during Stage 1 and BZA for only 90 days during Stage 2).
- The second key secondary objective is to demonstrate the tolerability of BZA in this population. This will include special focus with regards to fatigue as this is a major symptom for patients suffering from multiple sclerosis.
- The third key secondary objective is to document the safety of BZA in this population of patients.
- The fourth key secondary objective of this study is to help assess which secondary and tertiary outcomes are likely to be informative for future remyelinating trials in multiple sclerosis.

#### Additional Secondary Objectives:

- To evaluate the efficacy of BZA relative to placebo in increasing magnetization transfer ratios derived from magnetic resonance imaging of the brain during the period of exposure to active treatment.
- To evaluate the efficacy of BZA relative to placebo in reducing latency delay on multifocal visual evoked potentials during the period of exposure to active medication.
- To evaluate the efficacy of BZA relative to placebo at reducing radial diffusivity derived from diffusion tensor imaging as assessed by magnetic resonance imaging during the period of exposure to active medication.
- To evaluate the efficacy of BZA in reducing the EDSS score at the end of Stage 1 (Group A exposed to BZA for 90 days, Group B exposed to placebo for 90 days), as well the efficacy of BZA in reducing EDSS at the end of Stage 2 (after 180 days of BZA in Group A and 90 days of placebo + 90 days of BZA in Group B).
- To evaluate the efficacy of BZA relative to placebo in improving Symbol Digit Modalities Test (SDMT) performance at the end of Stage 1 and at the end of Stage 2.

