### 4 STUDY DESIGN

#### 4.1 Study Overview

This is a 6-month randomized, single center, double blinded, delayed start study in 50 patients with relapsing remitting multiple sclerosis and identified injury to the anterior visual pathway.

Patients will be randomized 1:1 into two groups: Group A and Group B. Group A will receive 180 days of Bazedoxifene while Group B will receive 90 days of placebo followed by 90 days of Bazedoxifene. Patients will receive two fixed oral tablets of 20mg Bazedoxifene (Conbriza) daily (to be taken at the same time). Patients will be permitted to remain on their standard disease modifying treatment during the course of the study.

Screening data will be reviewed to determine subject eligibility. Subjects who meet all inclusion criteria and none of the exclusion criteria will be entered into the study

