### 15.4 Analysis of Secondary Endpoints

Secondary endpoints will be analyzed using the same methods as primary endpoints.

Safety and tolerability data will be summarized by treatment group.

Adverse event rates will be coded by body system and MedDra classification term. Adverse events will be tabulated by treatment group and will include the number of patients for whom the event occurred, the rate of occurrence, and the severity and relationship to study drug.

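### The Stage 2 SDMT objective names a placebo comparator that no longer exists by then, and the MTR, radial diffusivity and multifocal VEP objectives do not say when placebo is the comparator

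*Combined protocol and SAP*

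**What the plan says.** Section 4.1 gives the treatment sequence: "Group A will receive 180 days of Bazedoxifene while Group B will receive 90 days of placebo followed by 90 days of Bazedoxifene". The synopsis entry for the control product likewise limits placebo to the first 90 days of the delayed-start group.

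Four of the additional objectives in Section 3.2 use placebo as the comparator:

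- SDMT: BZA "relative to placebo in improving Symbol Digit Modalities Test (SDMT) performance at the end of Stage 1 and at the end of Stage 2".
- MTR: "To evaluate the efficacy of BZA relative to placebo in increasing magnetization transfer ratios", with the window given as "during the period of exposure to active treatment".
- Radial diffusivity: "To evaluate the efficacy of BZA relative to placebo at reducing radial diffusivity derived from diffusion tensor imaging", with an equivalent window worded in terms of active medication.
- Multifocal VEP: BZA against placebo in "reducing latency delay on multifocal visual evoked potentials during the period of exposure to active medication".

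Other objectives state the contrast clearly. The primary objective (Section 3.1) compares the two groups over their first 90 days. The first key secondary objective (Section 3.2) compares Group A with Group B at 180 days and spells out each group's exposure. The EDSS bullet does the same for the end of Stage 2 and does not mention a comparison with placebo.

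On analysis, Section 15.4 says "Secondary endpoints will be analyzed using the same methods as primary endpoints". Section 15.3 names a mixed effects linear model with clustering by eye, but no time point, contrast or period term. Section 15 defers detail to a later SAP.

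**The concern.** At the end of Stage 2 nobody is assigned placebo, so an objective that asks for efficacy against placebo at that time has the wrong comparator. An analyst who follows it literally would label an early-versus-delayed-start difference as placebo efficacy. In the other direction, a Day 180 null could be read as no efficacy when Group B has simply caught up.

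For MTR, radial diffusivity and multifocal VEP, the window is tied to exposure and not to a stage or a day. Active exposure lasts 180 days in one group and 90 in the other, and the two start at different times. The text does not say which part of it is to be set against placebo.

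These are cognitive, imaging and electrophysiological outcomes of the kind that the fourth key secondary objective wants judged for use in future remyelination trials. A mislabelled contrast would carry into that judgement.

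**Working it through.** The plan gives no figure for these four outcomes, so there is none to reproduce. The 90% power in Section 15.6 concerns P100 latency at 3 months. The main check sets each objective's comparator against what each group receives.

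**Step 1. Comparator by stage (Section 4.1 and synopsis).**

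| Period | Group A | Group B | Concurrent placebo? |
|---|---|---|---|
| Stage 1, Days 0–90 | BZA | placebo | yes |
| Stage 2, Days 90–180 | BZA | BZA | no |

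**Step 2. What can be estimated.** Appendix 1 schedules SDMT and MRI at Baseline, Month 3 and Month 6. A randomised placebo contrast at Month 3 therefore exists for SDMT, MTR and radial diffusivity. For VEP, Appendix 1 lists every visit without saying whether multifocal recording is included, and the synopsis names only full-field VEP. The same Stage 1 contrast is available for multifocal VEP if it is recorded at Baseline and Month 3. At Month 6 the randomised contrast is early versus delayed start for all four outcomes.

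**Step 3. The exposure window.** Read literally, active exposure is Days 0–180 in Group A and Days 90–180 in Group B. Concurrent placebo covers the first 90 of Group A's 180 days and none of Group B's 90.

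**Step 4. What the Day 180 contrast measures.** Let f(t) be the true benefit after t days of BZA. Assume that 90 days of BZA has the same effect whether it starts at Day 0 or Day 90. Then the Day 180 difference, A minus B, is f(180) − f(90):

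- effect complete by Day 90: f(180) = f(90), so the difference is 0;
- linear accrual: f(180) = 2f(90), so the difference is f(90);
- no effect until after Day 90: f(90) = 0, so the difference is f(180).

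**Step 5. Illustration of a Day 180 null.** The documents give no SD for any outcome. Assume the standardised Day 90 effect that 90% power with 25 per group implies (normal approximation, two-sided 0.05): d = (1.960 + 1.282) × √(2/25) = 0.917. If the Day 180 difference is 0, 25, 50, 75 or 100% of that effect, the chance of a significant result in favour of Group A is 2.5%, 12.5%, 36.7%, 68.1% or 90%. The same effective drug can thus produce anything from a near-certain null to a likely positive result at Day 180, depending only on how fast its effect accrues.

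**Step 6. Illustration of pooling.** No section specifies this analysis. If all BZA time were set against Group B's placebo time, there would be 25 + 25 + 25 = 75 patient-intervals on BZA and 25 on placebo, and 50/75 = 67% of the BZA intervals would have no concurrent placebo. With SDMT retest gains g1 and g2 in the first and second intervals, the bias in mean change is (g1 + 2g2)/3 − g1 = (2/3)(g2 − g1). For assumed gains of (2, 1), (3, 1) and (4, 0) points this is −0.67, −1.33 and −2.67 points.

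**The case against.** The strongest reply is that this is loose wording and the design is sound. SDMT and the MRI measures have a randomised placebo contrast at Month 3. The Stage 1 half of the SDMT objective is answerable as it stands. The EDSS bullet just before SDMT uses the same two time points and spells out the delayed-start comparison, so a sensible analyst would read SDMT the same way. Because placebo and active drug coexist only in Stage 1, the exposure window can be read as Stage 1, and using the primary method points that way too. These are additional secondary objectives. The synopsis list of secondary endpoints includes MTR but not SDMT, radial diffusivity or multifocal VEP.

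Most of this stands, and it rules out several stronger conclusions that a reader might draw:

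- That the design cannot answer these objectives. It can, for Stage 1, and at Day 180 it still gives a valid randomised early-versus-delayed contrast.
- That the plan pools all active exposure. The text leaves the window undefined. Stage 1 only, each patient's own exposure, or Group B's placebo period against its BZA period are all possible readings.
- That the retest bias in Step 6 belongs to this plan. It rests on assumed gains and on an analysis that nobody has specified.
- That the Day 180 contrast can never equal the effect of 180 days of BZA. It does if nothing happens in the first 90 days.

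The reply does not rescue the SDMT wording for Stage 2. The objective states a comparator, the comparator is absent at that time, and Sections 15.3 and 15.4 do not correct it. The adjacent EDSS bullet shows that the right wording was available.

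**Conclusion.** The point holds at the level of secondary objectives. The SDMT objective for the end of Stage 2 is wrong as written: the comparator it names ended at Day 90, and the randomised contrast is 180 versus 90 days of BZA. The MTR, radial diffusivity and multifocal VEP objectives do not define when placebo is the comparator, and read literally they extend into a stage without one.

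The mismatch itself rests only on the treatment sequence and needs no assumption. The interpretation as f(180) − f(90) assumes that the effect does not depend on when BZA starts. The power figures in Step 5 and the pooling figures in Step 6 are illustrations under stated assumptions. The primary objective, the first key secondary objective and the EDSS bullet are not affected.

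**What to change.** In Section 3.2, and correspondingly in Section 15.4:

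1. For SDMT, MTR, radial diffusivity and multifocal VEP, define BZA relative to placebo as change from Baseline to Day 90, Group A versus Group B, to match Section 3.1. Use this in place of the wording about the period of active exposure.
2. Restate the SDMT objective for Stage 2, and any Stage 2 analysis of the other three, as Group A versus Group B, early versus delayed start. Report it as the effect of the earlier or additional 90 days of BZA and not as efficacy against placebo.
3. Report Group B's change from Day 90 to Day 180 as an uncontrolled within-group description.
4. Leave the EDSS bullet's two contrasts as they are.
5. State in Appendix 1 whether the VEP entry includes multifocal recording, so that item 1 can be carried out for that outcome.

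Items 1 to 4 are rewording and need no new visits or data for SDMT and MRI. The price is that Stage 2 results support a weaker claim than the objectives now state.
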